7.1.8. Additional Analysis of Adverse Events

The incidences of drug hypersensitivity, injection site reactions, immune-mediated autoimmune disorders, and flu-like symptoms will be examined. The AE preferred terms or higher level terms (HLTs) corresponding to these events will be determined through the following MedDRA search terms (MST):

- A) Hypersensitivity (MedDRA preferred terms that match any of those in MST list “KUR_Hypersensitivity”)
- B) Injection site reactions (TEAEs with HLT=’Injection site reactions’ or ‘Administration site reactions NEC’ [as defined by MST list “KUR_Injection site reactions”])
- C) Immune-mediated/Autoimmune Disorders (MedDRA preferred terms that match any of those in MST list “KUR_Immune-mediated disorders”)
- D) Flu-like Symptoms as defined in MST list for “Flu-Like Symptoms”. A separate table will be created for flu-like symptoms related to any of the study drugs.

The number and percentage of participants who experienced the above events (1 table for each AE of interest) will be summarized separately for each population by treatment group and PT.

A corresponding listing for each participant population will be provided for each of the 4 types of AEs.

7.2. Laboratory Evaluations

Laboratory data collected during the study will be analyzed and summarized using both quantitative and qualitative methods. Summaries of laboratory data will be provided separately for each population by treatment group (active group within each cohort and all participants [within population] assigned to placebo) for the Safety Analysis Set. All data collected after the first dose date of study drug will be included. The analysis will be based on values reported in conventional units. When values are below the limit of quantitation (BLQ), they will be listed as such, and the imputed value will be used for the purpose of calculating summary statistics. Hemolyzed test results will not be included in the analysis, but they will be listed in by-participant laboratory listings.

A by-participant listing for laboratory test results will be provided for each participant population by cohort, participant ID, and visit in chronological order for hematology, coagulation, serum chemistry, urinalysis, screening serology tests (HBV tests [for healthy participants], HIV-1 and HCV), and FSH and pregnancy testing (for females only). Values falling outside of the relevant reference range and/or having a severity Grade of 1 or higher according to CTCAE Version 5.0 will be flagged in the data listings, as appropriate.

No formal statistical testing is planned.

7.2.1. Summaries of Numeric Laboratory Results

Descriptive statistics will be provided separately for each participant population by treatment group (active group within each cohort and all participants [within population] assigned to placebo) and visit for selected laboratory tests (hematocrit, hemoglobin, lymphocytes, neutrophils, white blood cells [WBC], platelets, alanine aminotransferase [ALT], aspartate aminotransferase [AST], alkaline phosphatase [ALP], total bilirubin, creatine kinase [CK], serum glucose, total cholesterol, lactate dehydrogenase [LDH], creatinine, eGFR_{CG}, and international normalized ratio [INR]) as follows:

- Baseline values
- Values at each postbaseline visit
- Change from baseline at each postbaseline visit

A baseline laboratory value will be defined as the last measurement obtained on or prior to the first dose of study drug. Change from baseline to a postbaseline visit will be defined as the visit value minus the baseline value. The mean, SD, median, Q1, Q3, minimum, and maximum values will be displayed to the reported number of digits; SD values will be displayed to the reported number of digits plus 1.

Median (Q1, Q3) change from baseline by visit will be plotted using a line plot for: lymphocytes, neutrophils, WBC, platelets, ALT, AST, and CK. Plots will be produced separately for each population with a line displayed for each treatment group (active group within each cohort and all participants [within population] assigned to placebo).

7.2.2. Graded Laboratory Values

The CTCAE, Version 5.0, will be used to assign toxicity grades (0 to 4) to laboratory results for analysis. Grade 0 includes all values that do not meet the criteria for an abnormality of at least Grade 1. For laboratory tests with criteria for both increased and decreased levels, analyses for each direction (i.e., increased, decreased) will be presented separately.

7.2.2.1. Treatment-Emergent Laboratory Abnormalities

Treatment-emergent laboratory abnormalities are defined as values that increase at least 1 toxicity grade from baseline at any time postbaseline. If the relevant baseline laboratory value is missing, any abnormality of at least Grade 1 observed postbaseline will be considered treatment emergent.

7.2.2.2. Summaries of Laboratory Abnormalities

The following summaries (number and percentage of participants) for treatment-emergent laboratory abnormalities will be provided separately for each participant population by treatment group (active group within each cohort and all participants [within population] assigned to placebo) for each lab test. Participants will be categorized according to the most severe postbaseline abnormality grade for a given lab test:

- Graded laboratory abnormalities
- Grade 3 or 4 laboratory abnormalities

For all summaries of laboratory abnormalities, the denominator is the number of participants with ≥ 1 nonmissing postbaseline value for the lab test of interest.

A by-participant listing of treatment-emergent laboratory abnormalities, and Grade 3 or 4 laboratory abnormalities will be provided by participant population, cohort, participant ID, and visit in chronological order. This listing will include all test results that were collected throughout the study for the lab test of interest, with all applicable severity grades and abnormal flags displayed.

7.2.3. Liver-related Laboratory Evaluations

Liver-related abnormalities after initial study drug dosing will be examined and summarized separately for each participant population by treatment group (active group within each cohort and all participants [within population] assigned to placebo) using the number and percentage of participants who were reported to have the following laboratory test values for postbaseline measurements:

- ALT and/or AST $> 5 \times$ ULN
- ALT $> 3 \times$ ULN and Total Bilirubin $> 2 \times$ ULN
- AST $> 3 \times$ ULN and Total Bilirubin $> 2 \times$ ULN

The summary will include data from all postbaseline visits. For individual laboratory tests, subjects will be counted once based on the most severe postbaseline value. For composite endpoints, participants will be counted once when the criteria are met at the same postbaseline visit date. The denominator is the number of participants in the Safety Analysis Set who have at least 1 nonmissing postbaseline value for all relevant tests at the same postbaseline visit date.

A listing of participants who met at least 1 of the criteria above will be provided with ALT, AST, total bilirubin and alkaline phosphatase displayed in the listing for the participant's entire laboratory profile during study. Values that met criteria will be flagged in the listing.

7.3. **Body Weight, Height, and Vital Signs**

For vital signs data (systolic and diastolic blood pressure, pulse, and temperature) collected on the same date as an injection (eg, Days 1 and 57 for Cohorts 1 and 2; Days 1, 29, 57 and 85 for Cohorts 3, 4, 5, and 6; and Days 1, 29, 57, 85, 113 and 141 for Cohorts 7 and 8) both “Pre-Dose” and “Post-Dose” measurements were to be collected per protocol and will be displayed in summary tables. For displays of BMI and weight and visits where injections were not administered, only the pre-dose measurement [VSTPT_STD='VSPD' in VSPERF eCRF] will be presented in by visit displays (ie, no splitting for “pre-dose” and “post-dose” is required at any of the visits for weight or BMI or for non-injection days where vital signs were collected).

Descriptive statistics will be provided separately for each participant population and will be presented by treatment group (active group within each cohort and all participants [within population] assigned to placebo) for body weight, BMI, and vital signs (both pre-dose and post-dose measurements will be displayed for vital signs collected on dosing dates) as follows:

- Baseline value
- Values at each postbaseline time point [visit or visit/timepoint on injection days for vital signs data]
- Change from baseline at each postbaseline time point [visit or visit/timepoint on injection days for vital signs data]

A baseline value will be defined as the last available value collected on or prior to the first dose of study drug. Change from baseline to a postbaseline visit will be defined as the postbaseline value minus the baseline value. For vital signs collections on the same date as a study drug injection, separate summary statistics will be displayed for “Day X Pre-dose” and “Day X Post-Dose” for by visit displays. Vital signs visits with no injections administered will be displayed under “Day X Pre-dose”; and for all weight and BMI data.

A by-participant listing of vital signs will be provided separately for each participant population and be sorted by cohort, participant ID number, visit, date and time in chronological order (and the timepoint [pre-dose or post-dose] will be displayed in the listing). Body weight, height, and BMI will be provided in a separate listing.

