4.3. Phase 1b Virally Suppressed CHB Participant Inclusion/Exclusion Criteria

4.3.1. Inclusion Criteria

Phase 1b participants must meet all of the following inclusion criteria at screening (or as stated otherwise) to be eligible for participation in this study:

- 1) Have the ability to understand and sign a written ICF, which must be obtained prior to initiation of study procedures.
- 2) Assigned male sex at birth or female sex at birth (and be nonpregnant and nonlactating).
- 3) Participants assigned male at birth and participants assigned female at birth and of childbearing potential who engage in heterosexual intercourse must agree to use protocol-specified methods of contraception as described in Appendix 11.4
- 4) Be aged 18 through 65 years, inclusive, at enrollment.
- 5) Have a calculated BMI of ≤ 32.0 kg/m².
- 6) Documented evidence of CHB based on one of the following:
 - a) Positive HBsAg or HBV DNA at least 6 months prior to the screening visit; OR
 - b) Historical liver biopsy consistent with CHB infection available.

- 7) Quantitative HBsAg greater than the LLOQ and ≤ 5000 IU/mL at screening.
- 8) Have no evidence of advanced fibrosis by FibroScan (defined as FibroScan < 9 kPa within 6 months of screening). If a historical FibroScan is not available, this can be done at screening.
- 9) 12-lead ECG evaluations must be without clinically significant abnormalities as assessed by the investigator.
- 10) Nondiabetic with a hemoglobin A1c $< 6.5\%$.
- 11) Must be willing and able to comply with all study requirements.
- 12) Have a calculated CL_{cr} of at least 60 mL/min (using the Cockcroft-Gault method {[Cockcroft 1976](#)}) based on serum creatinine and actual body weight as measured for:
 - Participant assigned **male** at birth:
$$\frac{(140 - \text{Age [years]}) \times (\text{Weight [kg]})}{72 \times (\text{Serum Creatinine [mg/dL]})} = CL_{cr} \text{ (mL/min)}$$
 - Participant assigned **female** at birth:
$$\frac{(140 - \text{Age [years]}) \times (\text{Weight [kg]}) \times 0.85}{72 \times (\text{Serum Creatinine [mg/dL]})} = CL_{cr} \text{ (mL/min)}$$
- 13) Alanine aminotransferase $< 3 \times$ ULN; international normalized ratio (INR) \leq ULN; albumin ≥ 3.5 g/dL; direct bilirubin $\leq 1.5 \times$ ULN; platelets within the normal limit.

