- If the ALT elevation is confirmed, the central clinical laboratory will conduct reflex testing for HIV, HBV DNA, qualitative HBV serology (HBeAg and HBeAb; HBsAg and HBsAb), HAV IgM, HCV RNA, anti-HDV IgM, HDV RNA, HEV IgM, antinuclear antibody, antimitochondrial antibody, smooth muscle antibody, and liver/kidney microsome

Based on the results of the confirmatory tests, the following study treatment modifications are recommended.

Table 11. ALT Elevation Monitoring and Toxicity Management

Liver Toxicity Criteria	Action
Confirmed, ALT and or AST $\geq 10 \times$ ULN without evidence of hepatic toxicity as defined below	Cohort 5 to 7: Stop investigational product. Evaluate adherence to NA therapy and review recent HBV DNA results. Evaluate for other causes of hepatotoxicity. Participant must be monitored weekly or more frequently if clinically indicated until ALT returns to nadir. Investigative product may be restarted when ALT $< 5 \times$ ULN upon discussion with medical monitor. Dosing may also be reinitiated upon the recommendations of the SRT.
Persistent ALT and or AST $> 2 \times$ baseline and $\geq 5 \times$ ULN without evidence of hepatic toxicity, as defined below	Cohorts 5 to 7: Continue investigative product. ALT should be evaluated every 2 weeks or more frequently as clinically needed, until values return to nadir.
Confirmed ALT and or AST $> 2 \times$ nadir, with evidence of hepatic toxicity, defined as any one of the following confirmed laboratory abnormalities: Total bilirubin $> 2 \times$ baseline or nadir AND $> 2.5 \text{ mg/dL}$ in the absence of Gilbert's disease Elevated INR > 0.5 above baseline AND $>$ ULN Abnormal serum albumin $> 1 \text{ g/dL}$ decrease from baseline	Cohorts 5 to 7: Permanently discontinue investigational product. Evaluate adherence to NA therapy and review recent HBV DNA results. Evaluate for etiology of ALT elevation. Participant should be monitored weekly until ALT $< 5 \times$ ULN, and total bilirubin, INR, and albumin values return to normal or baseline levels. Liver biopsy may be performed based on investigator's clinical judgment to determine etiology.

ALT = alanine aminotransferase; AST = aspartate aminotransferase; DNA = deoxyribonucleic acid; HBV = hepatitis B virus; INR = international normalized ratio; NA = nucleos(t)ide analogue; SRT = Safety Review Team; TAF = tenofovir alafenamide; ULN = upper limit of normal

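### SAP 7.2.3 counts its ALT/AST-plus-bilirubin composites only on a shared visit date, so a lagged case with peak ALT and AST at or below 5 x ULN reaches neither its liver table nor its liver listing

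*SAP*

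**What the plan says.** SAP 7.2.3 tabulates three postbaseline liver criteria by treatment group:

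- Row 1: "ALT and/or AST $> 5 \times$ ULN"
- Row 2: "ALT $> 3 \times$ ULN and Total Bilirubin $> 2 \times$ ULN"
- Row 3: "AST $> 3 \times$ ULN and Total Bilirubin $> 2 \times$ ULN"

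For rows 2 and 3 it adds: "For composite endpoints, participants will be counted once when the criteria are met at the same postbaseline visit date". The denominator carries the same restriction: all relevant tests must be available on one postbaseline date. The listing depends on the same rows: "A listing of participants who met at least 1 of the criteria above will be provided with ALT, AST, total bilirubin and alkaline phosphatase", shown for the whole study. No time window, any-date row or sensitivity version is given.

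Protocol 7.7.4 uses the same thresholds for its combined liver criterion, in its opening triggers and in its reference to Hy's law. It does not say that the two results must come from one date.

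**The concern.** Bilirubin may first be seen raised after the enzymes have begun to fall. When the two peaks straddle a sampling interval, no single date shows both, and the composite rows stay empty for that participant. Row 1 rescues the case only if ALT or AST exceeded 5 x ULN. Because the listing is triggered by the same rows, it does not act as a safety net.

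The analysis is descriptive, with about 8 active participants per cohort, and laboratory abnormalities are part of the primary endpoint. A single case therefore matters, and the table meant to bring enzyme and bilirubin results together could show none when one occurred.

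**Working it through.** The plan states no figure on this point, so there is none to reproduce. The check applies the SAP rules as written to hypothetical profiles, then looks at the sampling schedule and the effect of one case.

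**Rules (values in multiples of ULN; TB = total bilirubin)**

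- Row 1: on some date, ALT > 5 or AST > 5.
- Row 2: on some date, ALT > 3 and TB > 2.
- Row 3: on some date, AST > 3 and TB > 2.
- Liver listing: row 1 or row 2 or row 3.
- Comparison rule: TB > 2 on or after a date with ALT or AST > 3.

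**Hypothetical profiles (ALT / AST / TB)**

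| Profile | First date | Second date | Row 1 | Row 2 | Row 3 | Liver listing | Comparison rule |
|---|---|---|---|---|---|---|---|
| A | 4.5 / 2.8 / 1.0 | 2.5 / 1.8 / 2.4 | no | no | no | **no** | yes |
| B | 8 / 6 / 1.0 | 2.5 / 1.8 / 2.4 | yes | no | no | yes | yes |
| C | 4.8 / 2.8 / 1.0 | 3.2 / 2.1 / 2.4 | no | yes | no | yes | yes |
| D | 4.5 / 3.5 / 2.4 | 2 / 1.5 / 1.2 | no | yes | yes | yes | yes |
| E | 5.0 / 4 / 1.0 | 3.0 / 2 / 2.4 | no | no | no | **no** | yes |
| F | 5.1 / 4 / 1.0 | 3.0 / 2 / 2.4 | yes | no | no | yes | yes |

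A and E are lost from both outputs. B and F lose only the composite count. C is kept because ALT is still above 3 when bilirubin is raised. Loss from both outputs therefore needs all of:

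1. peak ALT and peak AST both at or below 5;
2. at least one of them above 3;
3. bilirubin above 2 only on a later date, when neither enzyme is above 3.

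**Sampling intervals (chemistry days from the schedules of assessments and SAP Table 3-1)**

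| Cohorts | Nominal gaps between successive panels (days) |
|---|---|
| 1, 2 | 14, 14, 28, 14, 14, 56, 84 |
| 3 to 6 | eight of 14, then 56, 84 |
| 7, 8 | twelve of 14, then 56, 84 |

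Visit windows change these somewhat: Day 99 (±1) to Day 113 (±3) can be as short as 110 − 100 = 10 days. The shortest possible version of a late gap is Day 169 (±7) to Day 225 (±7) in Cohorts 7 and 8: 218 − 176 = 42 days. A 30-day window starting at one late panel would therefore never reach the next scheduled one.

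**Effect of one case (group sizes from SAP 1.3; placebo pooled within population under SAP 3.2: 5 x 2 = 10 and 3 x 2 = 6; exact Clopper-Pearson 95% intervals)**

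| Group | None counted | One counted | Change |
|---|---|---|---|
| Active cohort, n = 8 | 0% (0 to 36.9%) | 12.5% (0.3 to 52.7%) | 12.5 points |
| Phase 1a placebo, n = 10 | 0% (0 to 30.8%) | 10% (0.3 to 44.5%) | 10 points |
| Phase 1b placebo, n = 6 | 0% (0 to 45.9%) | 16.7% (0.4 to 64.1%) | 16.7 points |

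**The case against.** The strongest reply is that little is hidden. SAP 7.2 lists every chemistry result by participant in date order and flags out-of-range values; 7.2.1 summarizes ALT, AST, total bilirubin and INR by visit; 7.2.2.2 tabulates the worst postbaseline grade for each test on any date. A reader might infer that a lagged case vanishes from the report, or that 7.2.3 is the only liver output. Neither is so. What stands is that none of those other outputs pairs the enzymes with bilirubin.

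Extra samples may also close the gap. For Cohorts 5 to 7, protocol 7.7.4 asks for elevated on-treatment ALT to be confirmed, ideally within 3 days, although its opening sentence refers to the above-5 and combined triggers. Protocol 7.3.2 and 7.7 ask for follow-up of clinically significant abnormalities and adverse events, and SAP 7.2.3 uses all postbaseline visits. This lowers the chance of a miss, but one early repeat need not capture a later bilirubin rise.

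Other stronger readings are not supported:

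- **The SAP contradicts the protocol.** It does not. Protocol 7.7.4 is silent on timing and guides management; the SAP adds a reporting restriction.
- **Liver injury is the main foreseen hazard.** Protocol 1.5 names injection-site and systemic reactions, hypersensitivity and immune-mediated conditions, not hepatic injury.
- **The share of cases missed can be quantified.** Any modelled share depends on assumed enzyme peaks, decay rates and bilirubin lags, none of which is in the documents. With no lag the two rules agree.
- **The rule also over-counts, and a condition that the composite was not met at baseline would cure it.** Phase 1b entry limits direct rather than total bilirubin ("direct bilirubin $\leq 1.5 \times$ ULN; platelets within the normal limit"), so a stable total bilirubin of 2.1 x ULN with ALT moving from 2.9 to 3.1 x ULN would be counted. A baseline condition would not remove it, because 2.9 is below the ALT threshold. The listing already shows the whole profile.
- **Table 11 must be tabulated.** Its category "with evidence of hepatic toxicity, defined as any one of the following confirmed laboratory abnormalities" belongs to a dosing-management table, not an endpoint. Laboratory abnormalities that lead to discontinuation are recorded as adverse events (protocol 7.6), and adverse events leading to discontinuation are tabulated (SAP 7.1.7.1).

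**Conclusion.** The point holds as a narrow gap in reporting sensitivity: a participant who satisfies conditions 1 to 3 is in neither the 7.2.3 table nor the 7.2.3 listing. It is not an arithmetic error or an inconsistency between the documents, and a same-date rule is a legitimate choice for one row.

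The size is known only per case: 12.5 points in a planned active group of 8. How often it would happen is unknown. The conclusion assumes that bilirubin can lag the enzymes by enough to fall on a different sampling date, and that no unscheduled panel shows both raised together. It is worth changing because the cost is low and the data are already collected.

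**What to change.** In SAP 7.2.3:

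1. Keep the two same-date composite rows.
2. Add a row for ALT, and one for AST, counting a participant when total bilirubin above 2 x ULN is observed on or after a postbaseline date with that enzyme above 3 x ULN. Accept any later postbaseline date, or a prespecified window that the sponsor justifies. If a window is used, its length should reflect the 56- and 84-day gaps in late follow-up, which a 30-day window would not span.
3. Match the denominator: participants with a nonmissing postbaseline value of that enzyme and a nonmissing bilirubin on the same or a later date, within the window if there is one.
4. Trigger the liver listing on any postbaseline ALT or AST above 3 x ULN. Show baseline values beside the profile, so that a bilirubin already raised at entry and unchanged is visible.

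The cost is a few sentences of SAP text and a small programming change. No extra samples are needed and participant management is unchanged. The drawback is that an occasional coincidental pair, more likely without a window, will be counted and must be explained from the listing.

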7.4. Prior and Concomitant Medications and Disease-Specific Medications

Prior and concomitant medications collected at screening and during the study will be coded using the current version of the World Health Organization (WHO) Drug Dictionary.

7.4.1. Prior Disease-Specific Medications

Prior disease-specific medications are defined as medications taken before a participant took their first dose of study drug that were recorded on the HBV Treatment eCRF (applicable only for virally suppressed CHB participants in Cohorts 5 to 7). A summary of Hepatitis B Prior Medications will be summarized by treatment group (active group within each cohort and all participants [within population] assigned to placebo) for virally suppressed CHB population.

Disease-specific prior (e.g., anti-HBV) medications will be listed on the Prior and Concomitant HBV medications listing.

For the purposes of analysis, any medication with a start date prior to the first dosing date of study drug will be included as a prior medication regardless of the stop date. If a partial start date is entered the medication will be considered prior unless the month and year (if day is missing) or year (if day and month are missing) of the start date are after the first dosing date for study drug. Medications with a completely missing start date will be included as prior medications, unless otherwise specified.

